## 7.4.1 Dosage and Formulations

**Test Device:** PN40082 (manufactured by Prollenium Medical Technologies) is a clear, colorless gel in 1.0 mL pre-filled syringes with 25 mg/mL of stabilized hyaluronic acid and lidocaine 0.3% w/w. The study device will be provided by the Sponsor.

**Comparator device:** RV001 (manufactured by Prollenium Medical Technologies) is a clear, colorless gel in 1.0 mL pre-filled syringes with 25 mg/mL of stabilized hyaluronic acid to be used with LMX4, a topical lidocaine. The study device will be provided by the Sponsor. LMX4 will be provided in commercial stock packaging by the Sponsor

**Comparator device:** RV001 (manufactured by Prollenium Medical Technologies) is a clear, colorless gel in 1.0 mL pre-filled syringes with 25 mg/mL of stabilized hyaluronic acid to be used alone. The study device will be provided by the Sponsor.

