### 7.4.3 Study Device Administration

Subjects are physically masked (blindfolded) just prior to and during all injection procedures including the application of the LMX4 or inert cream to prevent observation of the syringes containing study device and the topical product. Any unblinded investigators and staff should be reminded NOT to discuss the treatment in the presence of the subject. Subjects will maintain the unique subject number previously assigned in Protocol PRO 2018-02 and PRO 2018-03.

The subject should be positioned in a seated position and may be reclined to as much as 45°.

Any makeup should be removed with a gentle cleanser or a specific makeup remover product (such as Neutrogena Cleansing Makeup Remover Facial Wipes).

The non-vermillion areas of the upper and lower lips should be prepared by gentle washing with a surgical scrub product (Chlorhexidine, Technicare, etc.).

To maintain the subject blinding, the upper and lower lip, upper and lower vermillion and any planned injection areas in or around the mouth corners should be covered with a liberal application of either the Sponsor provided inert cream or the topical anesthetic according to the randomization code. The designated cream product should be applied in a layer thick enough

that no skin or lip color is visible through the product. Investigators should use as much cream as necessary to achieve this result and not be limited to the contents of one tube of product.

Wait 15 minutes before treatment administration.

The anesthetic cream or inert cream should be removed by wiping firmly with a dry gauze before injecting. Only the area to be immediately treated should be wiped clear of cream. Areas not yet treated should remain covered with cream until moments prior to undergoing injection.

To prepare the syringes for use, the investigator should attach one of the needles included in the subject study device kit in a firm manner. The plunger should be gently depressed to express any unwanted air until a small droplet of implant material appears at the tip of the needle.

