- 10. If blanching of the tissues is observed during or directly after injection and becomes a concern, the area may be gently massaged. If blanching persists, contact the Medical Monitor.
- 11. The lips should be augmented to achieve the maximum desirable appearance for both the treating investigator and the subject. Subjects should be provided a small hand mirror to observe the results and further injections conducted until maximum benefit has been obtained. Care should be taken to ensure that the lips are symmetric from right to left and that the upper and lower lips have relative proportionality.
- 12. The perioral area should be corrected AFTER the upper and lower lips have been corrected. Some correction of perioral rhytids may occur with lip augmentation, thus it is best to address any remaining perioral correction needs after the lip injections have been completed.
- 13. If the treated area is swollen directly after the injection, an ice pack can be applied on the site for a short period if the investigator deems it appropriate. Ice should be used with caution if the area is still numb from anesthetic to avoid thermal injury.
- 14. Subjects should be encouraged to avoid a recumbent position for several hours after injections to reduce swelling. The use of ice, cold packs or other therapies to reduce swelling should only be performed at instruction of the investigator. The subject should be instructed to contact the site if substantial swelling occurs.

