## 7.4.4 Blinding of Study Device

Injections of the study device are performed by the unblinded Treating Investigator. The blinded Evaluating Investigator is not allowed to retrieve study supplies or to be present during opening of the study supplies or during the injections. The Treating Investigator is not to have any discussion with the Evaluating Investigator or subjects regarding the treatments.

Subjects are blinded to treatment assignment. Subjects are physically masked (blindfolded) just prior to and during all injection procedures to prevent observation of the syringes containing study device.

Subjects, investigators, the Sponsor's staff conducting the study, and members of the administrative team will not have access to individual subjects' treatment assignments. In the event of an emergency that requires breaking of the study blind, the randomization code will be maintained by each investigator that can be opened to reveal the study device.

See Section 7.9.10.2 for a description of the method of unblinding a subject during the study if such action is warranted.

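### Does the mid-session mirror check defeat the blindfold that keeps subjects masked for the pain score?

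*Combined protocol and SAP*

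**What the plan says.** Section 7.4.3 (Study Device Administration) sets the masking rule: "Subjects are physically masked (blindfolded) just prior to and during all injection procedures including the application of the LMX4 or inert cream". It gives the reason directly afterwards: "to prevent observation of the syringes containing study device and the topical product". Section 7.4.4 (Blinding of Study Device) repeats the rule with a narrower purpose that names only the syringes: "Subjects are physically masked (blindfolded) just prior to and during all injection procedures to prevent observation of the syringes containing study device".

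Item 11 of the injection techniques in Section 7.4.3 then says: "Subjects should be provided a small hand mirror to observe the results and further injections conducted until maximum benefit has been obtained". The same sentence is item 10 of the injection techniques in Appendix 2 (PN40082) and item 24 in Appendix 3 (RV001).

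Two further instructions bear on what the mirror would show. On the cream, Section 7.4.3 says: "Areas not yet treated should remain covered with cream until moments prior to undergoing injection". On the order of treatment, item 12 says: "The perioral area should be corrected AFTER the upper and lower lips have been corrected".

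The Schedule of Activities and the Visit 1 list in Section 7.7.1 contain no masking or unmasking step.

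**The concern.** Read together, the sections ask for two things that cannot happen at the same moment. The subject is to be blindfolded for the injections, and is also to look in a mirror part-way through them. The mask has to come off for the mirror, and the text gives no exception, no sequence and no instruction about the supplies. The rules against discussing treatment in Sections 7.4.3 and 7.4.4 deal with talk, not sight.

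What is at stake is the injection pain score. Pain is in the study's title and objective, it is marked by the subject on a VAS (Section 7.6.23), and it is the one efficacy measure that Section 8.2 sets out to compare between arms. A subject who learned, or thought they had learned, that they had no anesthetic could score pain differently for that reason alone.

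**Working it through.** No arithmetic applies. The documents give neither a chance of recognition nor a size of bias, so the check is a comparison of the passages.

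**1. Do the two rules exclude each other?** The mask is required shortly before and during injection and cream application. If that means one unbroken period from first cream to last needle, item 11 cannot be carried out. If it means whenever injecting is about to happen or is happening, both rules can be followed: inject, pause, unmask, look, mask again, inject. The second reading gives effect to every sentence, and the requirement to mask shortly before injecting puts the blindfold back on before any further needle.

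**2. Does a site know what to hide during the pause?** Yes. Section 7.4.3 names the syringes and the topical product. It does not describe the mechanics, but the aim is explicit.

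**3. What could be seen if a site were careless?**

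- *Gel and syringe.* In Section 7.4.1 each device "is a clear, colorless gel in 1.0 mL pre-filled syringes with 25 mg/mL of stabilized hyaluronic acid". The lidocaine in PN40082 is not described as changing its appearance.
- *Needles.* Section 7.4.5 packs PN40082 with 30G needles and RV001 with 27G, but supplies 30G needles for use in both RV001 arms. The needle in use is therefore of the same gauge throughout. The difference lies in the unused needles in the RV001 tray. To gain from it, a subject would have to notice the gauge and know which device is packed with which.
- *Cartons.* The labels are described in the same terms for all arms.
- *LMX4 container.* Section 7.4.1 says: "LMX4 will be provided in commercial stock packaging by the Sponsor". This is the plainest cue, and it is covered by the stated purpose of the blindfold.
- *Cream on the face.* Untreated areas stay covered, and the perioral area comes after the lips, so cream may be visible in the mirror. Every arm has a cream, used expressly to keep the subject masked. Seeing cream is uninformative unless the inert cream looks different from LMX4 and the subject knows how. The documents do not describe its appearance.

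**4. Does the mirror check precede the pain scores?** For the second score this is the natural reading, since it is taken 15 minutes after the last injection. For the first it is an inference. The Schedule of Activities and Sections 7.7.1 and 7.8 place it immediately after treatment, which puts it after the mirror. The Synopsis and Section 7.1 say it is taken at the time of injection, and no passage orders the first score against the mirror check.

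**5. Is the mirror the only moment of sight?** No. The subject must see to mark the VAS immediately after treatment and again at 15 minutes. Supplies have to be out of view then too, and the same ordinary care covers all these moments. Item 13 of the injection techniques also recognises that the area may still be numb from anesthetic, a cue that no blindfold removes.

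**The case for a change.** The strongest argument for a change is that the plan itself treats subject masking as important. It uses a blindfold, an inert cream and a treatment-guess question (Section 7.6.24), yet says nothing about the one point in the session where the mask must come off. Reading the blindfold rule as allowing a pause removes the conflict but still leaves the handling of supplies unwritten. The guess question comes at Visit 2 or early termination, so it cannot prevent a lapse on Day 1. One or two sentences would fill the gap at almost no cost.

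The silence is real, and that part stands. If the sponsor were revising these sections anyway, a clarifying sentence would do no harm. But it would only write down what the stated purpose already asks of sites. It would not cover the VAS-marking moments unless it went further, and it would leave the cream question open. Section 7.6.1 refers to other study instructions and Section 7.9.9 to a treatment SOP. Neither is available here, and either may already describe the sequence, so it cannot be said that sites have no instruction.

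Asking the guess question on Day 1 as well would not help. The answer would partly reflect the pain just felt, so it could not separate lost masking from an anesthetic that works. It might also influence later self-reports and anchor the guess planned for Visit 2.

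**Conclusion.** No change to the plan is needed. The mirror check and the blindfold rule are not expressly reconciled, but they can be followed together, and the protocol says what must stay hidden. This is a gap in written procedure that competent sites fill in the obvious way.

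No unblinding or bias is shown, and no number can be put on either. Section 8.1 has results summarised descriptively, and the protocol names no primary endpoint or hypothesis test. The point therefore concerns only how much trust to place in the pain comparison, not an error rate.

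The conclusion rests on two assumptions: that sites keep syringes, trays and cream tubes out of view whenever the subject is unmasked, and that subjects cannot tell the inert cream from LMX4 by looking at it. The second cannot be checked from these documents. If the creams were plainly distinguishable to subjects, masking of the LMX4 arm would be weaker, and a reader of the pain results should bear that in mind.

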## 7.6.23 Subject Pain Score – Visual Analog Scale

Pain from the injection session will be assessed by the subject using a 100-mm VAS scale from 0 = no pain to 100 = worst possible pain at Visit 1/Day 1 immediately after the injection, 15 minutes post the last injection of the session, and at Visit 2. Subjects will be asked the question "How would you rate your pain from the injection of study material?" and will respond by placing a mark on the VAS. (Figure 3)

Figure 3 Visual Analog Scale for Subject Assessment of Pain

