### 7.8 Efficacy Endpoints

Efficacy will be evaluated by the Subject Pain Score immediately after treatment, 15 minutes after treatment, and at Visit 2. Efficacy will also be evaluated by LFGS, POL, pGAI, iGAI, and Swelling Assessment.

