## 7.9 Assessment of Safety

## 7.9.1 Safety Endpoints

Safety of the treatment with PN40082 or RV001 with topical anesthetic, or RV001 will be evaluated by the nature, severity, and frequency of treatment-emergent adverse events (TEAEs). All AEs that occur during the study will be recorded whether or not they are considered to be related to treatment. A description of the AE will be recorded with the date of onset, date of resolution, severity of the AE, relationship to the study device, action taken, and the outcome. The frequency and type of AEs will be evaluated for each group based on the previous

treatments that they received in the PRO 2018-02 and PRO 2018-03 protocols, and the difference in AEs in this protocol (PRO 2019-02) between the subjects who received injections that contained lidocaine, and the group that was treated with topical lidocaine.

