#### 7.9.3 Definitions of Terms

#### 7.9.3.1 Adverse Event

An AE is defined as any untoward medical occurrence associated with the use of a drug/device in humans, whether or not considered drug/device-related (21 Code of Federal Regulations [CFR] 312.32 (a) and 803). An AE can therefore be any unfavorable and unintended sign (including an abnormal laboratory finding, for example), symptom, or disease temporally associated with the use of a drug/device, without any judgment about causality.

Expected adverse events are defined as the events that appeared at injection site subsequent to the first injection. Expected adverse events may include but are not limited to bruising, swelling, erythema, edema, and inflammation at injection site.

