#### 7.9.5 Monitoring Adverse Events

Each subject will be monitored for the occurrence of AEs, including SAEs, immediately after treatment initiation. Each subject will be followed for safety monitoring until discharged from the study. Follow-up procedures related to pregnancy or AEs or SAEs may continue beyond the end of the study.

Subjects will be questioned and/or examined by the investigator or a qualified designee for occurrence of AEs throughout the study. The presence or absence of specific AEs should not be elicited from subjects. In addition, subjects will be instructed to record AEs on the subject diary card during the 2 weeks after treatment, and on the subject diary card dispensed at Visit 2 for the remainder of the study. Subjects having AEs will be monitored with relevant clinical assessments and laboratory tests, as determined by the investigator.

AEs, actions taken as a result of AEs, and follow-up results must be recorded on the CRF, as well as in the subject's source documentation.

For all AEs that require the subject to be withdrawn from the study and SAEs, relevant clinical assessments will be repeated as clinically appropriate until final resolution or stabilization of the event(s).

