#### 8.2 Efficacy Analysis

Compare subject pain scores (VAS) between PN40082 and RV001 with topical anesthetic and RV001. Change from baseline will be summarized for LFGS and POL. Other efficacy variables include pGAI, iGAI, and Swelling Assessment at Visit 2/Month 1.

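### Optional ice for swelling can come before the 15-minute pain score; the protocol sets no order and asks for no clock time, so ice use before the score may not be identifiable by arm

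*Combined protocol and SAP*

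**What the plan says.** **Ice.** Section 7.4.3, Injection Techniques, item 13 states: "If the treated area is swollen directly after the injection, an ice pack can be applied on the site for a short period". The sentence goes on to make this depend on the investigator's judgement, and item 14 limits ice to the investigator's instruction. Item 13 adds: "Ice should be used with caution if the area is still numb from anesthetic to avoid thermal injury". The same permission appears in Appendix 2 (item 12) and Appendix 3 (item 26). Those two items omit the judgement clause, but the item after each keeps the limit to the investigator's instruction.

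**Pain score.** Section 7.6.23 schedules the VAS immediately after injection, again "15 minutes post the last injection of the session", and at Visit 2. Section 7.8 makes all three efficacy endpoints: "Efficacy will be evaluated by the Subject Pain Score immediately after treatment, 15 minutes after treatment, and at Visit 2". Section 8.2 sets the comparison: "Compare subject pain scores (VAS) between PN40082 and RV001 with topical anesthetic and RV001".

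**Recording.** Section 7.4.7 has other treatments entered on the CRF with their indication, and section 7.6.6 has them reviewed at every visit and call. Swelling is a named expected event: "Expected adverse events may include but are not limited to bruising, swelling, erythema, edema, and inflammation at injection site". An adverse event is described "with the date of onset, date of resolution, severity of the AE, relationship to the study device, action taken, and the outcome" (section 7.9.1), and section 7.9.5 adds: "AEs, actions taken as a result of AEs, and follow-up results must be recorded on the CRF".

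**The concern.** Comparative injection pain is a stated objective. The protocol already standardizes other things that could affect pain: every arm gets an active or inert cream with a 15-minute wait, and 30G needles replace the 27G needles packed with RV001. Ice before the 15-minute score has no such control.

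Cooling may lower a pain rating. If subjects on RV001 alone were iced more often before the score than subjects in a lidocaine arm, the 15-minute contrast would shrink. If a lidocaine arm were iced more, the contrast would grow. To judge this afterwards, one must know who was iced before the score, and the protocol does not ask for that. The immediate score would normally precede ice and is largely unaffected. The Visit 2 score is not plausibly affected.

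**Working it through.** The plan gives no figure on this point, so there is none to reproduce. The check has three parts.

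**1. Can ice precede the score, and would the record show it?**
- Item 13 places ice directly after injection, and the score follows 15 minutes after the last injection. Ice can fall between them.
- The schedule (section 2), section 7.6.23, the Visit 1 list (section 7.7.1) and the ice items in section 7.4.3 and Appendices 2 and 3 neither put the score before ice nor ask for an ice time.
- The other-treatment record asks for name and indication. The adverse event record asks for dates of onset and resolution. When ice and score fall within the same quarter-hour, a date cannot give their order.

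Ice use as such can therefore be captured, perhaps incompletely. Its order relative to the score cannot be read from what the protocol requires.

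**2. Is there a route to different use by arm?**
- The trigger is swelling, and the documents give no reason to expect swelling to differ by arm.
- The decision is discretionary. Item 13 names only the investigator, but the decision falls most naturally to the person injecting, who is unblinded (section 7.4.4).
- The numbness caution bears mainly on PN40082 (lidocaine in the gel) and RV001 with LMX4. It advises care and does not withhold ice.

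Different use is plausible, not shown.

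**3. How large could the shift be?** Let p be the share of subjects iced before the score and r the VAS reduction from ice. For the contrast RV001 alone minus a lidocaine arm:

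observed difference = true difference − (p for RV001 alone − p for the lidocaine arm) × r

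The documents give neither p nor r. With assumed values, in either direction:

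| Difference in ice use | r | Shift |
|---|---|---|
| 0 points | any | 0 mm |
| 10 points | 5 to 10 mm | 0.5 to 1.0 mm |
| 20 points | 5 to 10 mm | 1.0 to 2.0 mm |
| 40 points | 10 mm | 4.0 mm |
| 50 points (extreme) | 20 mm (extreme) | 10 mm |

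For scale, the Synopsis expects fewer than 158 subjects and section 7.4.2 allocates 1:1:1. Since 158/3 = 52.7, there are at most about 52 per arm. With an assumed SD of 20 to 25 mm, the 95% half-width of a two-arm difference is 1.96 × SD × √(2/n):
- n = 52: 1.96 × 20 × √(2/52) = 7.7 mm; with SD 25, 9.6 mm.
- n = 30 (assumed): 1.96 × 20 × √(2/30) = 10.1 mm; with SD 25, 12.7 mm.

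A 7.7 mm shift would need a difference in ice use of 7.7/10 = 77 points if r = 10 mm, or 7.7/20 = 38.5 points if r = 20 mm. Shifts up to 4 mm lie inside sampling error at either size. The extreme 10 mm case slightly exceeds it at 52 per arm.

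**The case against.** The strongest case against the point is this. Ice needs visible swelling, is brief, and requires an investigator's decision under one rule for all arms. All arms receive a 25 mg/mL hyaluronic acid gel, so swelling need not differ. Section 7.6.23 asks about pain from the injection, not current pain, so later cooling may not change the answer. Every size above is assumed, and section 8.1 makes the results descriptive. The Visit 1 CRF and the separate detailed SAP are not in the documents, so a time field or an ice table may exist.

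Most of this stands, and it keeps the point small. It does not remove the gap in the protocol text. Nothing there sets the order or requires a clock time, and an unseen form may or may not make up for that. That a shift lies within sampling error does not make it harmless, since it is systematic.

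Two stronger readings are tempting, and the documents support neither. A reader might infer that ice use goes unrecorded, so that no difference between arms could be seen. Sections 7.4.7, 7.6.6, 7.9.1 and 7.9.5 give routes by which it can be recorded and compared. A reader might also infer that the 15-minute comparison is biased. That would need both different icing by arm and an effect of ice on the answer, and neither is documented.

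**Conclusion.** The point holds as a matter of sequence and timing. Following the protocol as written, discretionary ice can precede a compared pain endpoint, and the required records may not show which subjects had ice before the score. Only the 15-minute VAS is materially exposed, chiefly in the contrasts with RV001 alone. The direction is unknown. The size is also unknown and probably small: 0 to 4 mm under moderate assumed inputs, and 10 mm only if a 50-point difference in use meets a 20 mm effect of ice. These sizes rest on assumed ice use, effect, SD and, for the smaller case, number per arm. The change is a cheap improvement in interpretability; the gap does not threaten the study.

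**What to change.** - In section 7.4.3 item 13, section 7.6.23, Appendix 2 item 12 and Appendix 3 item 26, state that in all arms the 15-minute VAS is taken before any ice unless ice is medically needed. Changing only the protocol body would leave the appendices in conflict with it.
- On the Visit 1 CRF, record ice (yes/no) and its start time, so that it can be set against the time of the score.
- Tabulate ice use before the 15-minute score by arm. Label any summary that leaves out iced subjects as a sensitivity analysis only, because ice use arises after randomization.

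The cost is one sentence in four places, two CRF fields and one table. The downside is that optional ice is delayed by up to about 15 minutes, with the exception for medical need. The change has to be in place before subjects are treated, because the order cannot be reliably reconstructed later if times were not collected.
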